#### 6 STUDY INTERVENTION

Study intervention is defined as any investigational intervention(s), non-investigational product(s), marketed product(s), placebo, or medical device(s) intended to be administered to a study participant according to the study protocol.

Refer to the Investigator's Brochure for more detailed information regarding the storage, preparation, destruction, and administration of each treatment.

## 6.1 Study Intervention(s) Administered

## **6.1.1** Investigational Products

[figure not shown]
M254 will be supplied to the study site by Momenta or its agent for dosing by IV administration. Details of dose preparation will be provided in the Pharmacy Manual.

All participants will receive study drug as an IV infusion. A peripheral IV catheter will be inserted before dosing for administration of study drug. M254 is administered by IV infusion at a rate of up to a maximum of [CC] (see Section 6.1.1.1 for more details).

Subjects and patients should be hydrated prior to the start of infusion with approximately 2 glasses of liquid to avoid a possible thromboembolic event. Additionally, subjects and patients should be mobilized immediately following the end of infusion to decrease the risk of thromboembolic events.

The date, time, and volume of administration of all doses are to be recorded.

For Part A, the placebo to be used is commercially available Glucose 5% solution for injection.

#### 6.1.1.1 M254 and IVIg Infusion Rate

M254 and IVIg is administered by IV infusion at a rate of up to a maximum of CCI whichever is lower (CCI is less than infusion rates recommended for

Compound: M254 Protocol: MOM-M254-001

Protocol Date and Version:8 Global 28 April 2020

[figure not shown]
IVIg). After completion of the infusion, the IV line should be flushed with approximately 50 mL of 5% dextrose in water (D5W) within 10 minutes of completion of the infusion to ensure that the entire intended dose of drug product has been infused and none is retained in the IV tubing; other methods for ensuring accurate dosing may be used upon agreement of the Sponsor. Additional dosing information is provided in the study Infusion Manual.

The initially-planned infusion rate schedule is described in Table 6-1; the infusion rate and duration at an infusion rate may be increased or decreased as part of the dose escalation decision with the restriction that it may not be >4 mg/kg/min.

Table 6-1. M254 and IVIg Infusion Rate

Start Time (minutes relative to Infusion Start)	End Time (minutes relative to Infusion Start)	Infusion Rate (mg/kg/minute)
0	30	0.5
30	60	1
60	90	2
90	360	4

Two specific examples of implementing the above infusion rate table for the rate are:

#### **6.1.2** Non-investigational Products

Not applicable.

## 6.2 Preparation/Handling/Storage/Accountability

## 6.2.1 Study Drug Packaging and Storage

Study drugs must be stored in a secure area (eg, a locked refrigerator or locked cabinet within a refrigerator), protected from moisture and light, and be stored at CCI

Further instructions regarding storage and handling, dose preparation, and administration of study drugs are detailed in the Pharmacy Manual.

Compound: M254 Protocol: MOM-M254-001

Protocol Date and Version:8 Global 28 April 2020

## 6.2.2 Study Drug Accountability

In accordance with Good Clinical Practices (GCP), each study site will account for all study drug supplies. The pharmacy will maintain accurate records, including information regarding the receipt and subject administration of all test articles. Reasons for departure from the expected dispensing regimen must also be recorded. At the completion of the study, to satisfy regulatory requirements regarding drug accountability, all study drug will be reconciled. Drug will be retained and returned to the drug distribution center. Destruction at site may be considered per site standard operating procedures (SOPs) and approval of the Sponsor. The arrangement for destruction must be communicated to the Sponsor or delegated contract research organization (CRO). Refer to the Pharmacy Manual for further information.

## 6.3 Measures to Minimize Bias: Randomization and Blinding

Part A is double-blind, sponsor open; subjects and the Investigator will be blinded to individual subjects' treatment throughout this part. The sponsor will be unblinded throughout this part (and throughout the study). Specified individuals at the Investigator site (such as the unblinded pharmacist) will be unblinded throughout this part (and throughout the study). When interacting with the Investigator or site personnel, the sponsor will maintain care in the communication not to unblind.

Parts B, C, and D are open-label investigations; patients and Investigators will not be blinded throughout these parts of the study.

In the event of a Quality Assurance audit, the auditor(s) will be allowed access to unblinded study intervention records at the site(s) to verify that dispensing has been done accurately.

A randomization schema will be developed for Part A and Part C and managed by the pharmacy at PRA in Netherlands for the study. The process will be described in detail in the applicable study plan.

# **6.4** Study Intervention Compliance

Administration of each IV infusion of study drug and all assessments will be performed by qualified personnel under the direction of the Investigator. Clinic personnel will confirm that study drug was administered and record start and end time of each infusion. Deviation(s) from the prescribed dosage regimen will be recorded in the electronic case report form (eCRF).

## 6.5 Concomitant Therapy

Subjects participating in the study should avoid concomitant administration of any new medications other than antihistamine or acetaminophen (or corticosteroids for moderately severe acute reactions) during the course of the study, except as prescribed for newly-emerging AEs. Participants must abstain from taking prescription or nonprescription drugs (including vitamins and dietary or herbal supplements) throughout the study, unless, in the opinion of the Investigator and sponsor, the medication will not interfere with the study.

Compound: M254 Protocol: MOM-M254-001

Protocol Date and Version:8 Global 28 April 2020

Premedication should not be administered systematically. If a patient develops an infusion reaction related to the M254 or IVIg infusion, standard management should be applied (see the Infusion Manual for detail).

During the study subjects should remain on the dose of the ITP medications they were on at screening.

Any medication or vaccine (including over-the-counter or prescription medicines, vitamins, and/or herbal supplements) that the participant is receiving at the time of enrollment or receives during the study must be recorded in the subject's eCRF along with:

- Reason for use
- Dates of administration including start and end dates
- Dosage information including dose and frequency

The Medical Monitor should be contacted if there are any questions regarding concomitant or prior therapy.

## **6.6** Dose-Cohort Study Escalation Rules

In this study, Parts A and B are dose-escalating; Parts C and D are not dose-escalating.

A dose escalation report (DER) will be provided by the Investigator to the Independent Ethics Committee (IEC) (where required) following completion of each dose level. The SRC will approve escalation to the next dose only if none of the stopping criteria have been reached, the safety and tolerability (and PD for Part B) out to Day 10 are acceptable, and there are no concerns regarding delayed significant AEs in earlier cohorts.

The minimum number of participants required to decide on dose escalation is 2 participants on active treatment (ie, a total of at least 3 subjects in Part A at all dose levels; and 2 patients in Part B); in Part B for dose levels precedented as tolerated with safety reviewed in Part A, only 1 subject is required for dose escalation though 2 will remain planned for the cohort.

Based on absence of significant toxicity in the Good Laboratory Practice (GLP) toxicity studies, escalation to the next higher dose will be up to approximately CCI. Based on emerging safety data (and PD data in Part B), lower or other intermediate dose(s) may be used, for instance when anticipated that after a planned dose escalation stopping criteria will be met. Pharmacokinetic data is not deemed necessary for dose escalation since IV dosing of this modified IgG has predictive exposures (100% bioavailability, volume of distribution [Vd] and clearance expected to be similar to endogenous IgG). There are no significant toxicity findings in the preclinical studies, and the maximum exposure in healthy volunteers is expected to remain well below exposures of the high dose (1000 mg/kg) used in GLP toxicity studies. In patients the maximum exposure is not expected to be above the high dose (1000 mg/kg) used in GLP toxicity studies.

Compound: M254 Protocol: MOM-M254-001

Protocol Date and Version:8 Global 28 April 2020

A more conventional 3+3 escalation design was considered but not employed in this study. A notable difference between the expectation of the design in the current study with 2 patients compared to a 3+3 design in literature is how the dose is used in the future. In the current study, [CC]

In a more conventional 3+3 design, a dose that triggers the 3+3 rule would be considered **tolerable**, and would be used for future study.

## 6.7 Stopping Rules

## 6.7.1 Dose-Cohort Study Stopping Rules

Dosing within a cohort and dose escalation to a next cohort will be halted pending evaluation by Sponsor and SRC recommendation if 1 of the following circumstances occurs and it is determined by the Investigator that the occurrence is possibly related to the administration of study drug:

- A serious adverse reaction (ie, a SAE considered at least possibly related to the study drug administration) in 1 subject.
- Grade 3 or higher AE per National Cancer Institute (NCI) CTCAE version 5.0 criteria (ie, severe nonserious AEs considered at least possibly related to the study drug administration) in 2 participants in the same cohort, or in 1 subject in the sentinel cohort.
- Grade 4 or higher grade AE per NCI CTCAE version 5.0 criteria.
- Other findings that, at the discretion of the Investigator in consultation with Sponsor's Medical Monitor and SRC recommendation, indicate that further dosing should be stopped.

When stopping rules for a cohort are met, the randomization code for participants meeting the stopping rules will be unblinded. If after de-blinding it is concluded that participants on active medication meet the stopping rules, dosing in the cohort will be stopped and no further dose escalation will be performed.

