## 4.1.1 Part A (Netherlands only)

Part A is a single-ascending-dose, randomized, double blinded sponsor unblind, safety, tolerability, and PK assessment of M254 or placebo in 6 cohorts of healthy volunteers. Planned doses include 3, 10, 30, 60, 120, and 250 mg/kg. In Cohort 1, 5 subjects will be enrolled with 3:2 (active:placebo) randomization. In all other cohorts, subjects will be randomized 3:1 (active:placebo) with total of 4 subjects in each cohort. There will be approximately 25 subjects in Part A. Up to 2 additional cohorts may be added based on findings in prior cohorts. Additional dosing cohorts may be added on the recommendation of the SRC.

Following screening to confirm eligibility to participate, subjects will be randomized to receive M254 or placebo. Please refer to Section 4.3.1 and Figure 1-2 for dosing details.

At the first dose level (3 mg/kg), a sentinel group of 2 subjects (1 M254, 1 placebo) will be dosed and closely monitored for 48 hours before dosing the remainder of the cohort (2 M254, 1 placebo). The subjects in this sentinel group will be closely observed by the Investigator for any safety signals for the first 48 hours following drug administration. The general tolerability of the study drug will be monitored during this time and the ECG recordings and vital signs data will be reviewed. In addition, any reported AEs will be considered by the Investigator. If the safety and tolerability results of the first 48 hours following dosing for the initial subjects are acceptable to the Investigator, the other subjects of Cohort 1 of Part A may be dosed. There will be no additional sentinel groups in the study beyond this cohort (Cohort 1 Part A)

Safety assessments will be conducted out to Day 28 post M254 dosing. The SRC will review all available safety data after each cohort has completed at least 10 days of assessments after the single dose of M254. Dose escalation will only proceed after the recommendation of the SRC.

The SRC will review all safety data for all subjects in Part A out to Day 28. Cohorts in Part B may start before the completion of Part A; however, prior to initiation of any cohort in Part B, either the same or a higher dose level will have been given in Part A and have a positive recommendation by the SRC, with the exception of doses greater than 250 mg/kg.

Compound: M254 Protocol: MOM-M254-001

Protocol Date and Version:8 Global 28 April 2020

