## 4.1.2 Part B (USA sites included)

Initiation of any cohort in Part B will only proceed on the recommendation of the SRC after safety data from Part A Cohort 4 at the 60-mg/kg dose level has been reviewed and confirmed by SRC.

Part B is a single-ascending-dose, fixed-sequence, open-label part to assess safety, tolerability, PK, and PD of M254 followed by 1000 mg/kg IVIg in approximately 4 cohorts of 2 ITP patients per cohort. Planned doses include 60, 120, 250, and 500 mg/kg. Up to 2 additional cohorts may be added based on findings in prior cohorts to better understand the safety of M254 and/or to better understand the efficacy to assist with dose selection for Part C. The maximum dose for Part B will not exceed 500 mg/kg. (The no-observed-adverse-event-level [NOAEL] of 1000 mg/kg was determined in the toxicology study in cynomolgus monkeys.) Additional patients to dosing cohorts may be added on the recommendation of the SRC.

Following screening to confirm eligibility to participate, patients will be dosed with M254. Please refer to Section 4.3.1 and Figure 1-3 for dosing details. There will be a 14-day safety monitoring period between enrollment of the first and second patients in the 500 mg/kg cohort.

Safety and platelet assessments will be conducted initially out to Day 28 post M254 administration. Patients will receive a fixed dose of IVIg at 1000 mg/kg on Day 29 if the patients' platelet count returns to  $\leq 15\%$  above baseline level. Patients whose platelets have not returned to  $\leq 15\%$  above baseline dosing level by Day 28 will have platelet determinations weekly until platelets return to  $\leq 15\%$  above baseline, up to 56 days postdose. If these conditions are not met by Day 57, IVIg will be administered, as long as the patients' platelets have returned to  $\leq 50 \times 10^9/L$ . If the platelets have not returned to  $\leq 15\%$  above baseline and are  $\geq 50 \times 10^9/L$ , the patient will complete Follow-Up assessments and be discharged from Part B. After dosing with IVIg, safety and the other assessments listed in the Schedule of Activities will be conducted for 28 days following IVIg administration.

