## **6.7.2 Dose Limiting Toxicities**

Dose-limiting toxicities will include any NCI CTCAE v.5 Grade 3 or higher adverse reaction occurring within 4 weeks following the administration of M254.

**Note:** Events considered by the sponsor as clearly unrelated to the study drug will not be considered a DLT, eg, thrombocytopenia related to ITP, accidents, and lab results attributed to other therapies or illnesses.

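### In a planned two-patient Part B cohort, the related nonserious Grade 3 stopping criterion cannot be met before both patients are dosed, and the 14-day stagger at 500 mg/kg has no hold criterion tied to it

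*Protocol*

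**What the plan says.** Protocol Section 6.7.1 lists four circumstances, each judged possibly related to study drug, that pause dosing in a cohort and escalation to the next one until the sponsor and SRC have reviewed:

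- "A serious adverse reaction (ie, a SAE considered at least possibly related to the study drug administration) in 1 subject".
- Grade 3 or higher events, explained as "ie, severe nonserious AEs considered at least possibly related to the study drug administration", occurring "in 2 participants in the same cohort, or in 1 subject in the sentinel cohort".
- A separate criterion for more severe events: "Grade 4 or higher grade AE per NCI CTCAE version 5.0 criteria", with no minimum count given.
- Other findings, at the investigator's discretion with the Medical Monitor and SRC.

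Section 6.7.2 defines a DLT as "any NCI CTCAE v.5 Grade 3 or higher adverse reaction" within four weeks of M254.

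Section 4.1.2 plans Part B as "approximately 4 cohorts of 2 ITP patients per cohort" and adds: "There will be a 14-day safety monitoring period between enrollment of the first and second patients in the 500 mg/kg cohort". Section 4.1.1 says of the 3 mg/kg healthy-volunteer cohort: "There will be no additional sentinel groups in the study beyond this cohort (Cohort 1 Part A". The same section requires each Part B dose to have been matched or exceeded in Part A, but exempts doses above 250 mg/kg.

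After one DLT in two patients, Section 4.1.2 makes repeating the cohort mandatory, whereas Section 6.7.3 makes it optional. Footnote b to Table 1-2 requires the first 500 mg/kg patient to attend the clinic on Day 15 and gives the 14-day interval as the reason.

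**The concern.** A cohort stopping rule exists partly to spare patients who have not yet been dosed. With a threshold of two in a cohort of two, the nonserious Grade 3 criterion cannot do that: when the count is reached, nobody in the planned cohort remains undosed. The one-subject alternative is tied to a sentinel cohort, and Part B has none.

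The gap is sharpest at 500 mg/kg. That dose is twice the highest planned Part A dose (500/250 = 2) and is exempt from the requirement for Part A precedent. The protocol's added safeguard is the 14-day gap between the two patients. A gap of this kind protects the second patient only if some finding during it would hold the second infusion. The plan calls a related Grade 3 reaction dose-limiting in one section, while the automatic Grade 3 criterion in the section before it does not respond to a single such event when it is nonserious.

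The rule also reads as if written for Part A. Section 6.7.1 closes with unblinding of the randomization code, which has no meaning in an open-label, fixed-sequence part.

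**Working it through.** The plan states no operating characteristic for the stopping rule, so there is no figure to reproduce. The check has three steps.

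**1. Can the nonserious Grade 3 criterion act between the two patients?**

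Inputs: threshold r = 2 (Section 6.7.1); planned cohort size n = 2 (Section 4.1.2); sentinel route unavailable in Part B (Section 4.1.1).

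- After the first patient, at most one participant can have had an event. Since 1 < 2, P(criterion met) = 0 for any event rate.
- Patients still undosed when the criterion is met: n − r = 2 − 2 = 0.

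These two results need no assumption about event rates.

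**2. How often would the criterion respond at all?**

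Let p be the chance that a patient has a related nonserious Grade 3 event, with patients independent. The documents give no value for p, so the range below is an assumption.

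- Criterion met after both patients: p²
- At least one event in the cohort: 1 − (1 − p)²
- Share of cohorts with an event in which the criterion is met: p² / [1 − (1 − p)²]

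| p (assumed) | Met after patient 1 | Met after both | At least one event | Share |
|---|---|---|---|---|
| 0.05 | 0 | 0.0025 | 0.0975 | 2.6% |
| 0.10 | 0 | 0.01 | 0.19 | 5.3% |
| 0.20 | 0 | 0.04 | 0.36 | 11.1% |
| 0.30 | 0 | 0.09 | 0.51 | 17.6% |
| 0.50 | 0 | 0.25 | 0.75 | 33.3% |

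At p = 0.20, for example, 0.04/0.36 = 11.1%. The table describes the rule as written. It does not argue for another threshold.

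**3. Does another provision cover a single nonserious Grade 3 event in the first patient?**

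- *Section 6.7.1, serious or Grade 4 or higher events:* these act on one event, but the event in question is neither.
- *Section 6.7.1, discretionary criterion:* it can act, but nothing obliges it to.
- *Section 8.3.5:* one moderate or severe systemic infusion reaction should prompt an SRC meeting on whether to continue dosing. Other kinds of Grade 3 reaction are not covered.
- *Section 6.7.4:* for four named types of event, it needs Grade 3 or greater related events in two or more patients, so one event alone does not trigger it.
- *Sections 4.1.2 and 6.7.3:* they address repeating the cohort after one DLT in two, not holding the second infusion.

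**The interval itself.** Day 15 minus Day 1 is 14 days, so footnote b fits an interval counted from the first infusion. Section 4.1.2 counts it between enrollments, and screening spans Day −28 to Day −2. The two starting points coincide only if enrollment falls at about the time of dosing. Separately, the four-week DLT window outlasts the 14-day stagger, so a DLT arising on about Days 15 to 28 could follow the second infusion under any trigger.

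**The case against.** The strongest reply is that the second patient is far from unprotected. A Grade 3 reaction that is also serious halts dosing after one subject, and Section 10.3.2 counts hospitalization and medically important events as serious. Grade 4 or higher events have their own criterion. Discretion is itself one of the listed circumstances, and Section 8.3.5 brings in the SRC after a single significant infusion reaction. All of this stands. It confines the point to nonserious Grade 3 events and to the absence of an automatic halt.

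It can also be said that DLTs and stopping rules serve different ends, so different thresholds need not conflict, and that part of the rationale for two-patient cohorts in Section 6.6 is redacted. That is fair. The difficulty is not that the thresholds differ. It is that this one cannot operate between two patients whom the protocol deliberately separates at 500 mg/kg. Nor is the criterion empty: two events in two patients still pause escalation below the top dose, and in a cohort expanded beyond two it could act before later patients are dosed. At the lower doses no stagger is specified, so the second patient may already have been dosed.

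A reader might infer that one DLT leaves escalation free to proceed. The documents do not support that. Section 6.6 also requires acceptable safety and tolerability to Day 10 and no concern about delayed significant events; Section 4.1.2 sends the cohort to repetition; and 500 mg/kg is the Part B maximum.

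A reader might also infer that the second patient could be infused before the first. That requires enrollment to mean entry into screening. Section 5.3 distinguishes consenting from being entered in the study, and footnote b points to an interval from infusion. The wording is loose; a reversed order is not what the plan describes.

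**Conclusion.** The point holds in a limited form. In an unexpanded two-patient Part B cohort, the related nonserious Grade 3 criterion of Section 6.7.1 spares no patient in that cohort, and a first-patient event of this kind triggers no automatic halt although it is a DLT. This follows from the cohort size, the threshold and the sentinel statement alone. The practical consequence is greatest at 500 mg/kg, the one staggered cohort, because no stated finding during the 14 days obliges the second infusion to wait.

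The documents do not support saying that a Grade 3 DLT triggers no halt of any kind, or that a given percentage of cohorts would be affected. The serious, Grade 4 or higher, discretionary and infusion-reaction routes remain, and every value of p above is assumed.

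Two smaller inconsistencies belong with it: mandatory versus optional repetition of the cohort after one DLT in two, and an interval counted from enrollment in the text but matched to a post-infusion visit in the schedule.

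**What to change.** Reconcile the following passages. The threshold and any clinical rule are for the sponsor and SRC, and none is proposed here.

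1. Reconcile Section 6.7.1 with the DLT definition in 6.7.2, the planned Part B cohort size and the 500 mg/kg stagger. State how 6.7.1 applies to the first 500 mg/kg patient, given the statement in 4.1.1 that there are no further sentinel groups.
2. Make Sections 4.1.2 and 6.7.3 agree on whether repeating the cohort after one DLT in two is required or optional.
3. State the event from which the 14-day interval runs, in the synopsis, Section 4.1.2 and Table 1-2 footnote b, so that it agrees with the Day 15 visit.

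The cost is protocol wording in a few sections. Depending on what the sponsor and SRC decide, there may occasionally be a short pause before a second patient's infusion. No analysis or sample size changes.
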